## List of abbreviations

AC	Anterior chamber cells
AE	Adverse event
ALT	Alanine transaminase
AMD	Age-related macular degeneration
AREDS	Age-Related Eye Disease Study
AST	Aspartate transaminase
AUC	Area under the concentration time curve
-hCG	Beta human chorionic gonadotropin
B:MI	Body mass index
bpm	Beats per minute
BUN	Blood urea nitrogen
CFR	(United States) Code of Federal Regulations
CK	Creatine kinase
CSR	Clinical study report
eCRF	Electronic case report / record form
EDC	Electronic data capture
	Confidential Information
ETDRS	Early treatment in diabetic retinopathy study
FAF	Fundus autofluorescence
FDA	Food and Drug Administration
FSH	Follicle stimulating hormone
GA	Geographic atrophy
GCP	Good clinical practice
GLP	Good laboratory practice
IB	Investigator's brochure
IMT	Immuno-Modulatory Therapy
IRB	Institutional Review Board
IV	Intravenous(ly)
IVT	Intravitreous(ly), intravitreal(ly)
LC/MS	Liquid chromatography/mass spectrometry

LDH	Lactate dehydrogenase
LLOQ	Lower limit of quantification
MAC	Membrane attack complex
MFC	Multifocal choroiditis
mmHg	Millimeters of mercury
MRSD	Maximum recommended starting dose
NOAEL	No-observed adverse effect level
NIU	Non-infectious intermediate-, posterior- or panuveitis
PD	Pharmacodynamics
PG	Pharmacogenomics
pH	Negative log hydrogen ion concentration
PK	Pharmacokinetics
PRN	Pro re nata (as needed)
RBC	Red blood cell/capillary
RPE	Retinal pigment epithelium
SAE	Serious adverse event
sd-OCT	Spectral domain ocular coherence tomography
SUSAR	Suspected unexpected serious adverse reaction
TME	Translational Medicine expert
VEGF	Vascular Endothelial Growth Factor
WBC	White blood cell
WHO	World Health Organization
WOCBP	Women of child bearing potential

## Glossary of terms

Screening	Point/time of subject/patient entry into the study; the point at which informed consent must be obtained (i.e., prior to starting any of the procedures described in the protocol)
Enrollment	Point/time of subject/patient randomisation into the study / assignment of a randomization number.
Investigational drug	The study drug whose properties are being tested in the study; this definition is consistent with US CFR 21 Section 312.3 and is synonymous with "investigational new drug".
Phase	A major subdivision of the study timeline; begins and ends with major study milestones such as, Screening, or Study Completion.
Treatment Period	A minor subdivision of the study timeline that divides phases into smaller functional segments, i.e., the time starting from Baseline prior first study drug administration until the last day prior the next Baseline, or the Study Completion visit.
Premature subject/patient withdrawal	Point/time when the subject exits from the study prior to the planned completion of all study drug administration and assessments. At this time all study drug administration is discontinued. Study Completion assessments must be completed.
Study drug	Any drug administered to the subject as part of the required study procedures; includes investigational drug and any control and comparator drugs.

## Corporate Confidential Information

## **Corporate Confidential Information**

## **Corporate Confidential Information**

## Corporate Confidential Information

## **Corporate Confidential Information**

## Corporate Confidential Information

## **Corporate Confidential Information**

# Corporate Confidential Information

## **Corporate Confidential Information**

# Corporate Confidential Information

# Corporate Confidential Information

# Corporate Confidential Information

# Corporate Confidential Information

## **Corporate Confidential Information**

## **Corporate Confidential Information**

---

**Protocol synopsis**

---

**LFG316**

---

**Title of study:** A randomized, active-controlled, open-label, multicenter proof-of concept study of intravitreal LFG316 in patients with active non-infectious intermediate-, posterior-, or panuveitis requiring systemic immunosuppressive therapy

---

**Objectives:**

## Primary objective(s)

- To assess the effect of intravitreal LFG316 Corporate Confidential Information on the protocol defined, Day 85 response rate in the study eye of patients who meet the inclusion criteria.

## Secondary objective(s)

- To assess the safety and tolerability of intravitreal LFG316 (5 mg q 4 weeks x 3 doses) in patients who meet the inclusion criteria. Corporate Confidential Information
- To assess the effect of intravitreal LFG316 Corporate Confidential Information on vitreous haze as measured on the Nussenblatt scale, ETDRS visual acuity, macular edema, presence or absence of chorioretinal lesions, and anterior chamber cells score in the study eye of patients who meet the inclusion criteria, and compare these between Baseline and Days 2, 8, 15, 29, 43, 57, and 85. Corporate Confidential Information
- To evaluate the serum concentrations of total LFG316 and total CS during the course of the study.

**Corporate Confidential Information**

**Study Design:**

Approximately 24 patients with active NIU, in at least one eye, requiring intensification of systemic immunosuppressive therapy will be enrolled and randomized in a 2:1 ratio to receive intravitreal LFG316. Throughout the study, the fellow eye may be treated as needed; except that certain systemic medications are prohibited (see [Section 5.5.7](#) and [Section 5.5.8](#)). There will be 1 screening and 8 scheduled visits over 85 days for a total of 9 site visits for all patients.

**Corporate Confidential Information**

Assessments are listed in the [Assessment schedule](#). Efficacy assessments (ocular assessments and photos) will be conducted by personnel masked to the treatment assignment. Low molecular weight non-steroidal immunosuppressive medications are allowed up to the baseline day as long as the dose has not changed in the 3 weeks prior to baseline, except for corticosteroid doses which may change.

## **Corporate Confidential Information**

## Patient Safety

Safety assessments will include ocular evaluations, adverse events, and serious adverse events. Cumulative safety listings will be reviewed by the Principal Investigator and the Novartis Medical Director periodically during the study, and *ad hoc* when necessary.

### Population:

Approximately 24 patients with active NIU requiring intensification of systemic immunosuppressive therapy will be enrolled.

### Inclusion/Exclusion criteria:

Full inclusion / exclusion criteria are presented in [Section 4.1](#) and [Section 4.2](#), respectively.

#### Key inclusion criteria:

- Male or female patients 18 years or older.
- Active NIU, in at least one eye, as defined below, in patients requiring intensification of systemic immunosuppressive therapy:
  - Vitreous haze at least 1+ on the scale of [Nussenblatt et al 1985](#), or
  - Chorioretinal lesions due to uveitis (*chorioretinal lesions due to infectious uveitis will exclude the patient*)
  - Patients who present with a flare and who are at the time of the enrollment on systemic corticosteroid or non-steroidal immunosuppressants will have their therapy tapered or stopped, respectively, at the time of intravitreal LFG316 administration.
- Visual acuity (ETDRS method) of 20 letters (20/400 Snellen equivalent) or better in the study eye.
- Female patients must not be pregnant or lactating and must, unless post-menopausal, use effective contraception as specified in [Section 4.1](#) of this protocol.
- Ability to provide informed consent and comply with the protocol.

#### Key exclusion criteria:

- Uveitis so severe that, in the investigator's judgment, it is too risky to test an experimental drug.
- Bilateral uveitis for which, in the opinion of the investigator, systemic immunosuppressive therapy is required to manage the inflammation in the fellow eye; use of local therapy in the fellow eye is acceptable and not an explicit exclusion (See [Section 5.5.7](#) for acceptable concomitant treatments)
- Uncontrolled glaucoma or ocular hypertension in either eye, defined as an intraocular pressure (IOP) >30 mmHg while on medication for the specific condition
- Forms of uveitis that may spontaneously resolve such as multiple evanescent white dot syndrome (MEWDS).
- In the opinion of the investigator clinically significant abnormality in screening laboratory results or electrocardiogram.
- In the study eye, cataract that is expected to interfere with study conduct or require surgery during the study.
- History of infectious uveitis or endophthalmitis in either eye.
- History of retinal detachment
- Patients taking corticosteroids or other systemic immunosuppressive medication for any other disease (e.g., asthma or other autoimmune disease) where the tapering of the immunosuppressant would not be safe because of the risk of exacerbation of the extraocular disease
- Any biologic immunosuppressive agent given via intravitreal, intravenous or subcutaneous route within 4-12 months of screening depending on the agent.

- Any intraocular surgery, intravitreal injection, periocular injection, or laser photocoagulation to the study eye within 90 days prior to dosing.

**Investigational and reference therapy:**

Approximately twenty-four (24) patients will be enrolled and will be randomized 2:1 to either LFG316 (n=16) Corporate Confidential Information

LFG316 will be administered to patients randomized to LFG316 on days 1, 29 and 57.

Corporate Confidential Information

- LFG316 solution for injection is a liquid solution provided in vials containing

**Rescue to Conventional Therapy throughout the study:**

Study drug will be discontinued and conventional therapy instituted for any patient that meets the following criteria in the study eye:

- Loss of >10 letters in best corrected visual acuity (BCVA) at any visit, as compared to baseline that, in the opinion of the investigator, is due to worsening of uveitis.
- Active vitritis, anterior chamber inflammation, or chorioretinitis at least 28 ±3 days after their last dose that, in the opinion of the investigator, is significantly worse as compared to the previous visit and requires alternate therapy
- Unilateral flare in fellow / non-study eye which does not respond to local treatment (including ozurdex® implant) or bilateral flare in both eyes which require the intensification of systemic immunosuppressive therapy.

**Concomitant medications/Significant non-drug therapies:**

Intravitreal administration involves certain protocol-specified anesthetics and antibiotics. See the full protocol for a complete list of concomitant, permitted, and prohibited medications.

Corporate Confidential Information

**Primary endpoint:** response rate at Day 85, LFG316 treatment arm.

A response will be defined by any one of the following criteria in the study eye:

- An improvement of 2 or more steps in vitreous haze, relative to baseline. For the purpose of "step" calculation, 0.5 shall count as one of the increments. Thus, improvement from a score of 2 to 0.5 or from 1 to 0 would constitute a 2-step improvement **or**,
- An improvement of 10 or more letters in visual acuity, relative to baseline **or**
- An improvement of 2 or more steps in anterior chamber cells, relative to baseline **, or**
- Resolution of chorioretinal lesions as determined by the investigator, **or**
- Change in central retinal thickness from baseline to Day 85 of 50 micrometer

Remission (complete response) will be defined as any patient who has a vitreous haze score of 0 or 0.5 in the study eye, who has an anterior chamber cell score of 0 and no chorioretinal lesions in the study eye and is off all immune modulatory therapy (systemic, corticosteroids and topical), without any worsening of uveitis during the trial.

**Secondary endpoints:**

- Mean changes in BCVA, vitreous haze score, AC cell score, and central retinal thickness on Days 2, 8, 15, 29, 57 and 85 for both eyes of all patients.
- Mean changes in BCVA, vitreous haze score, AC cell score, and central retinal thickness in LFG316 responders on Days 169, 253, and/or 281 (EOES)
- Percentage of eyes that respond (as per responder criteria) on days 2, 8, 15, 29, 57.
- AE and SAE rates on days 2, 8, 15, 29, 57 and 85 for all patients

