## **9.5 Analysis of secondary variables**

### **9.5.1 Efficacy / Pharmacodynamics**

Summary statistics for the secondary endpoints and their changes from baseline will be provided by treatment group and visit/time. Corporate Confidential Information

A longitudinal analysis of the secondary PD endpoints may be performed if deemed relevant. Graphical displays of mean time profiles may be constructed as appropriate.

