## **7 Statistical methods for Efficacy and Pharmacodynamic (PD) parameters**

### **7.1 Primary endpoint**

The primary endpoints are the response rate (proportion of patients that respond in the study eye) and the remission rate (complete response) at Day 85.

A response will be defined by any one of the following criteria in the study eye:

- An improvement of 2 or more steps in vitreous haze, relative to baseline. For the purpose of “step” calculation, 0.5 shall count as one of the increments. Thus, improvement from a score of 2 to 0.5 or from 1 to 0 would constitute a 2-step improvement or,
- An improvement of 10 or more letters in visual acuity, relative to baseline or,
- An improvement of 2 or more steps in anterior chamber cells, relative to baseline
- Resolution of chorioretinal lesions as determined by the investigator

Remission (complete response) will be defined as

- any patient who has a vitreous haze score of 0 or 0.5 in the study eye, who has an anterior chamber cell score of 0 and no chorioretinal lesions in the study eye and is off all immune modulatory therapy (systemic, corticosteroids and topical), without any worsening of uveitis during the trial.

The analysis of response rate and remission rate at Day 85 will be carried out on the efficacy analysis sets (Efficacy 1 and Efficacy 2), with the analysis on the Efficacy 1 analysis set being of primary interest.

The baseline value will be defined as Day 1 pre-dose value, or the screening values if the Day 1 pre-dose value does not exist.

The response rates and the 90% exact (Clopper-Pearson) confidence intervals in the LFG316 group Corporate Confidential Information will be reported. Corporate Confidential Information

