Percentage of patients that respond per response criterion (for criterion involving central retinal thickness, only if applicable) will be reported in each treatment group.

A separate set of summary tables will be produced for those subjects who participate in the LFG316 treatment extension, if deemed necessary.

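### The extension means lean favourable, through selection on a shared baseline and loss of data after rescue, so a good mean alone does not show sustained benefit

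*Protocol*

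**What the plan says.** The Protocol synopsis (Secondary endpoints) defines the extension result as "Mean changes in BCVA, vitreous haze score, AC cell score, and central retinal thickness in LFG316 responders on Days 169, 253, and/or 281 (EOES"). The bullet does not name the reference point. Protocol 9.5.1 supplies it: "Summary statistics for the secondary endpoints and their changes from baseline will be provided by treatment group and visit/time". SAP 7.1 fixes a single baseline: "The baseline value will be defined as Day 1 pre-dose value, or the screening values if the Day 1 pre-dose value does not exist".

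Response is an any-one rule in the synopsis: "A response will be defined by any one of the following criteria in the study eye". Three of its criteria are "An improvement of 2 or more steps in vitreous haze, relative to baseline", "An improvement of 10 or more letters in visual acuity, relative to baseline" and "An improvement of 2 or more steps in anterior chamber cells, relative to baseline". A lesion criterion follows. The protocol, but not SAP 7.1, also has a criterion on central retinal thickness. The Assessment schedule heads the extension columns as being for LFG316 responders.

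On analysis, SAP 7.2.1 offers only this: "A separate set of summary tables will be produced for those subjects who participate in the LFG316 treatment extension, if deemed necessary". That section runs on the Efficacy 1 set. Under SAP 5 a patient who stops or is rescued contributes to that set only up to that point. SAP 7.4 does not impute and treats missing values as missing at random. The visible text plans response rates up to Day 85 and none in the extension.

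**The concern.** Two mechanisms act in the same direction.

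- **Shared baseline.** A patient whose baseline reading happened to be poor is more likely to show a Day 85 gain and so to count as a responder. The same poor reading is subtracted again at Days 169 to 281, so part of the apparent gain persists whether or not the drug works.
- **Loss of relapsed patients.** A responder who worsens and is rescued leaves later summaries. The remaining patients are those who did well, and missingness that follows relapse is not at random in the sense the SAP assumes.

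The endpoint as printed names no comparator. The risk is that a favourable late mean in a small group of responders is reported as sustained benefit.

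**Working it through.** **Plan's own figure.** None is stated for this endpoint. The only design figures concern the Day 85 test in 16 LFG316 patients with a rule of 11 responders. I use 11 below only as an illustrative group size. (The error rates stated there fit 12 or more responders, with a false positive rate of 16.7% against 32.9% for 11 or more. That is a separate matter.)

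**Inputs from the documents.** Gain of 10 or more letters, any-one rule, one baseline (synopsis; SAP 7.1). Data end at rescue or discontinuation (SAP 5). Loss of more than 10 letters attributed to uveitis is one rescue criterion (Protocol 5.5.6.1).

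**Assumptions, not in the documents.** SD of change in acuity 7, 10 or 15 letters; equal correlation between visits; four criteria, the other three cut at the same number of SDs as acuity; correlation between criteria 0, 0.3 or 0.6.

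**Step 1: selection on acuity alone, no true change.** Write D85 = Y85 − Y0 and D169 = Y169 − Y0. The shared Y0 gives a correlation of 0.5, so E[D169 | selected] = 0.5 × E[D85 | selected], where E[D85 | selected] = SD × φ(c)/(1 − Φ(c)) and c = 10/SD.

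| SD | c | Expected Day 85 gain | Expected Day 169 gain |
|---|---|---|---|
| 7 | 1.43 | 7 × 0.1438/0.0766 = 13.1 | 6.6 |
| 10 | 1.00 | 10 × 0.2420/0.1587 = 15.3 | 7.6 |
| 15 | 0.67 | 15 × 0.3194/0.2525 = 19.0 | 9.5 |

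**Step 2: the any-one rule, no true change (simulation).** Many patients now qualify on another criterion, so the acuity bias shrinks. The Day 169 mean runs from +1.4 (correlation 0) to +4.8 letters (SD 15, correlation 0.6). The mean of 11 responders exceeds zero in about 63% to 97% of samples.

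**Step 3: does the mean respond to loss of effect?** True Day 85 gain of 10 letters, SD 10, correlation 0.3, any-one rule:

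| True state at Day 169 | Mean change, letters | Still meeting any criterion |
|---|---|---|
| Gain kept | +10.8 | 89% |
| Half kept | +5.8 | 71% |
| Fully lost | +0.8 | 47% |
| 5 letters below baseline | −4.2 | 24% |

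(The other criteria move by the same number of SDs.) The mean does track the effect.

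**Step 4: adding removal of relapsed patients.** Treat responders' Day 169 change as normal with mean m and SD s, and drop values below −10. The remaining mean is m + s × φ(a)/Φ(a), with a = (m + 10)/s.

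- Null, low end: m = 1.43, s = 7.4, a = 1.54; 1.43 + 7.4 × 0.129 = +2.4.
- Null, high end: m = 4.77, s = 14.4, a = 1.03; 4.77 + 14.4 × 0.278 = +8.8.
- Last row of Step 3: m = −4.2, s = 9.9, a = 0.59; −4.2 + 9.9 × 0.466 = +0.4. A true decline below baseline then reads as no change.

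This is an upper illustration. The rescue criterion also needs the investigator to attribute the loss to uveitis, and a value taken just before rescue may still be counted at that visit.

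**Step 5: the alternative summary.** Under no effect, 41% to 76% of responders still meet some criterion at Day 169. With SD 10 and correlation 0.3 the figure is 58%, against 42% in unselected patients, so the proportion is inflated too. It is also imprecise: 8 of 11 gives an exact 90% CI of 44% to 92%.

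**The case against.** A reader might infer that the mean is positive by construction and cannot reflect durability. The documents do not support that. A patient can qualify on haze, cells or lesions without gaining a letter, later means can be zero or negative, and Step 3 shows them falling when the effect is lost.

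A reader might also size the bias by selecting on acuity alone. With visit errors of SD 3 to 6 letters that gives +5.5 to +6.9 letters at Day 169. But under that model only 1.3% to 13% of patients would be selected, or 0.2 to 2.1 of 16. The plan works with response rates of 60% to 85% and an any-one rule, so that figure does not apply here.

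Three further points are fair. No visible text calls this a durability endpoint or attaches a test to it, and the stated efficacy comparisons end at Day 85. The extension entry rule and objectives may lie in redacted text. SAP 7.2.1 already plans haze and cell frequencies with a worsening category and individual acuity profiles, which could reveal relapse. However, that section uses Efficacy 1, so readings after rescue are absent there as well, and extension coverage is not explicit.

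What stands is that the baseline is shared, the endpoint text names no comparator, and the analysis set loses relapsed patients. None of that depends on the size of the bias.

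**Conclusion.** The point holds as a minor but inexpensive improvement. The extension means are biased in the favourable direction and should not on their own be read as sustained benefit. The no-effect acuity mean is about +1.4 to +4.8 letters, or about +2.4 to +8.8 if all patients more than 10 letters below baseline are removed. These values rest on assumed SDs and correlations and on responders being defined at Day 85, so they show direction and range only. The means remain useful as description because they fall when the effect is lost. The maintained-response proportion does not remove the shared-baseline problem. Its advantage is that every Day 85 responder stays in the denominator until the extension ends.

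**What to change.** Add as the main extension summary, in the synopsis endpoint list and SAP 7.2.1, the proportion of all Day 85 LFG316 responders who still meet the SAP 7.1 response definition at each extension visit, with an exact 90% CI.

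- Count rescue, discontinuation and missed scheduled visits as not maintained, with counts by reason. This departs from SAP 7.1, which leaves a patient with no assessed criterion as missing, so it must be written down.
- Leave out visits a patient was never scheduled to have. The and/or in the endpoint's list of days suggests that not everyone is due at every visit.
- Keep the mean changes as descriptive, beside the same patients' Day 85 means and the number rescued or stopped by each visit.
- State that the proportion is also affected by selection on the shared baseline and is imprecise at this size.

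The visible Ocular Assessment schedule already collects acuity, haze, cells and lesions at Days 169 and 253, so those visits need no new assessment. The cost is one endpoint wording and one table, and reported durability may look less favourable.

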## Corporate Confidential Information

**Sample size determination**

The target sample size for this study is approximately 24 patients, randomized in a 2:1 ratio

Power calculations are not based

upon a comparison between LFG316 Corporate Confidential Information but rather on the null hypothesis that the response rate in the LFG316 arm (PLFG) will not differ from the lower bound of the expected Corporate Confidential Information response rate which is assumed to be 60%. With 16 patients in the LFG316 arm, the null hypothesis  $H_0: PLFG \leq 0.60$  will be rejected in favor of  $H_1: PLFG > 0.60$ , if 11 / 16 patients in the sample are responders. Such a rejection rule has 17% false positive rate (incorrectly reject  $H_0$  when it is true) and 45% (80%, 92%) power to correctly reject  $H_0$  when the true PLFG is 70% (80%, 85%).

